Specific Aim #1: To define the levels of relationship satisfaction and sexual function among couples with the female partner having primarily: UUI symptoms and mixed urinary incontinence (urge predominant).

Hypothesis 1: Couples with (female partner) UUI will have lower levels of relationship satisfaction and sexual function based upon validated measures of sexual function and relationship cohesion.

Specific Aim #2: To measure the impact of successful treatment of UUI on the relationship.

Hypothesis 1: Successful treatment with Vesicare will result in improvement in relationship satisfaction and sexual function for both male and female partners.

We expect that the results of this prospective study will allow us to objectively quantify the degree to which intimate relationships are affected by UUI thus filling a critical gap in our knowledge. We also expect to demonstrate that successful treatment of UUI leads to an improvement in relationship satisfaction and sexual function.

Significance of the Proposed Work

Chronic illness places emotional, physical, and financial burdens upon both the patient and her partner, and can be a significant source of stress in a relationship. The symptoms of UUI inherently pose greater social challenges than those faced by women with other forms of pelvic floor disorders. For example, women with UUI may avoid social situations due to fear of having an accident or may be reluctant to participate in activities during which it may be difficult to find a bathroom. The resulting social isolation impacts both members of the dyad and may serve as a source of relationship discord. Changes in sexual function and perceived intimacy, including non-intercourse intimacy, as well as communication may be new sources of stress in a previously healthy relationship or may serve to amplify pre-existing relationship problems.

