The Dyadic Adjustment Score is a validated instrument for evaluation of adjustment in relationships between either married or unmarried cohabiting couples. It may be used at baseline to obtain a comprehensive description of the relationship and as an objective measure of change in the interaction between partners after an intervention. The DAS consists of a 32-item self-administered questionnaire that is not gender specific. It has four subscales: relationship satisfaction, cohesion, consensus, and affectional expression. The DAS takes 5-10 minutes to complete.

All women presenting with a chief complaint of 3 months of UUI or mixed urinary incontinence (MUI) with urge predominance to the Division of Female Pelvic Medicine & Reconstructive Surgery at Loyola University Medical Center who meet inclusion criteria will be approached for study participation. Women will receive a thorough explanation of the study, including the risks, benefits, and potential side effects of the study drug, and their questions will be answered. Women of childbearing age will be counseled that they should be using an effective method of birth control during the study. They will sign an informed consent document. They will also be given a 3 day voiding diary to be completed at home. Prior to completing the 3 day voiding diary, patients currently taking an anticholinergic medication will undergo a 2 week wash out period during which

they will not take any drug. They will also be given a letter describing the study to give to their partner.

Women with a diagnosis of UUI or MUI, urge predominant, who have consented to participate and whose partners consent to participate will return to the clinic with completed study questionnaires (PISQ-12, PFIQ-7, MESA, GRISS, and DAS).

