They will be given Vesicare 5mg with instructions for use. After 4 weeks of use, we anticipate that 50% of patients will note improvement. Those who do not feel that their symptoms are adequately controlled will have the option of increasing to 10 mg per day for the remaining 8 weeks of the study. After 12 weeks of medication use, patients will have a follow up visit, they will be asked to again complete all of the PISQ-12, PFIQ-7, MESA, GRISS, and DAS as well as the Overall Quality of Life Related to Urinary Incontinence Questionnaire. Male partners will also complete a second set of questionnaires either in the clinic or at home after their partner has undergone 12 weeks of treatment. Patients will be given a total of 16 weeks of Vesicare to allow for some variation in scheduling follow up and to ensure that they are currently taking Vesicare at the time that they complete their follow up questionnaires.

Subjects and Recruitment

Loyola's clinical research team is well-suited to successfully recruit women to this study. Our division has four clinical faculty members, all of whom are NIH funded investigators who participate in large clinical and surgical trials through the Urinary Incontinence Treatment Network and the Pelvic Floor Disorders Network. In addition, we have 4 full-time research nurses and a data entry manager. The entire group is fully supportive of this research.

Recruitment of men for studies on female urinary incontinence is a new area of research. This study would be the first to exam relationship dynamics from the perspective of the male partner using validated methods. Based upon a small pilot study of male partners that was conducted at our center, we believe that the recruitment of male partners is a feasible goal. Because there is no direct benefit to the male partner and given the personal nature of the data collected, compensation of the male partners (travel and parking) is reasonable and likely to give a more representative sample.

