Subjects will be recruited from all racial and ethnic groups. Race and ethnicity will be determined by self-reporting according to the guidelines of The Office of Management and Budget Directive No. 15. On the screening questionnaire, subjects will be allowed to choose from 2 ethnic categories, "Hispanic or Latina" and "Not Hispanic or Latina". They will also choose from 5 racial categories: American Indian or Alaska Native; Asian; Black or African American; Native Hawaiian or Other Pacific Islander; and White. Appropriate definitions will be included on the questionnaire.

Women will eligible for *inclusion* in the study if they are:

- Age \geq 18 years, and
- In a relationship with a male partner for at least 3 months, and
- Not pregnant (pregnancy test will be done at study enrollment) or planning to become pregnant, and

- Have a diagnosis of UUI or MUI, urge predominant, based on recall
- Are interested in medical management of their symptoms and are candidates for Vesicare, and
- Able to provide informed consent and complete the written questionnaires.

Women will **excluded** from participation in the study if they have:

- PVR > 200 ml at initial visit
- Significant outflow obstruction
- Persistent/recurrent UTI
- Bladder stones
- A diagnosis of chronic interstitial cystitis
- Undergone pelvic irradiation
- Current pelvic malignancy
- Narrow angle glaucoma
- Urinary or gastric retention
- Current use of a tricyclic antidepressant
- A neurologic diagnosis that could affect bladder function (MS)
- A diagnosis of chronic pelvic pain
- An active psychotic disorder

Women will also be **ineligible** for participation if they:

- Or their partner is non-English speaking
- Decline permission for the study team to approach their partner regarding participation

Statistical Analysis

Power Analysis

While the change in the overall GRISS score is the primary outcome in this study, the sample size for this study is based upon published research utilizing the DAS (i.e., which also measures relationship satisfaction).

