For Aim 1, baseline Golombok Rust Inventory of Sexual Satisfaction (GRISS) scores will be compared between matched male and female partners using a paired samples *t*-test. The difference between female and male responses will be assessed for normality using a QQ plot and for outliers using a boxplot. If parametric assumptions are violated, conclusions may be confirmed using a Wilcoxon signed-rank test.

For Aim 2 we will subtract participants' overall 3-month GRISS score from their overall baseline score and compare this change in GRISS between those who respond and do not respond to solifenacin using an independent samples *t*-test. As before, the normal distribution of the change score in each response group will be assessed graphically using a QQ plot and for outliers using a box-plot. If parametric assumptions are violated, conclusions may be confirmed using a non-parametric Wilcoxon rank-sum test.

Finally, healthy male partners of female participants also complete the GRISS at baseline and after their female partner completes approximately 12-16 weeks of solifenacin treatment for UUI symptoms. For these male partners, a change score will be calculated by subtracting their baseline score from the follow-up score. This change score will be compared between male partners of female participants who respond to solifenacin versus male partners of female participants who do not respond to solifenacin.

All statistical analysis will be conducted using SAS Version 9.4 (SAS Institutes, Cary, NC) with the input of a Biostatistician.

References

1. Shaw C. A systematic review of the literature on the prevalence of sexual impairment in women with urinary incontinence and the prevalence of urinary leakage during sexual activity. *Eur Urol*. 2002 Nov;42(5):432-40.
2. Hilton P. Urinary incontinence during sexual intercourse: A common, but rarely volunteered, symptom. *Br J Obstet Gynaecol*. 1988 Apr;95(4):377-81.

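### Aim 1's only test compares partners with each other, so it cannot support or refute the predicted lower levels, and no analysis of the DAS is specified for either aim

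*Combined protocol and SAP*

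**What the plan says.** Specific Aim #1 is worded as a description of levels in affected couples. Its hypothesis is directional: these couples are expected to show "lower levels of relationship satisfaction and sexual function based upon validated measures of sexual function and relationship cohesion". It does not say lower than whom. The Methodology and the eligibility criteria under Subjects and Recruitment admit only women with urge or urge-predominant mixed incontinence, together with their partners.

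For Aim 1, the Statistical Analysis Plan says that "baseline Golombok Rust Inventory of Sexual Satisfaction (GRISS) scores will be compared between matched male and female partners using a paired samples" t-test, with a signed-rank test on the same difference if parametric assumptions fail. Nothing else is specified for Aim 1.

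Specific Aim #2 predicts that successful treatment "will result in improvement in relationship satisfaction and sexual function for both male and female partners". The plan analyses this through change in GRISS by response group, for women and for male partners.

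The Methodology says of the DAS that "It has four subscales: relationship satisfaction, cohesion, consensus, and affectional expression", and that it may serve "as an objective measure of change in the interaction between partners after an intervention". Both partners complete it at baseline. At 12 weeks, for women, "they will be asked to again complete all of the PISQ-12, PFIQ-7, MESA, GRISS, and DAS", and "Male partners will also complete a second set of questionnaires". The Power Analysis names change in overall GRISS as the primary outcome but says that "the sample size for this study is based upon published research utilizing the DAS (i.e., which also measures relationship satisfaction". The Statistical Analysis Plan does not mention the DAS.

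**The concern.** There are two gaps.

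First, the test does not match the hypothesis. Whether affected couples score lower is a question of level and needs something outside the sample to compare with. Whether a woman and her partner score differently is a question of discordance within the couple. Either result of the paired test is compatible with either truth about the hypothesis.

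Second, relationship satisfaction and cohesion are named in the hypotheses, yet the only instrument described as having a cohesion subscale has no planned analysis. Relationship claims under both aims would then rest on GRISS alone, or on DAS analyses chosen after the data have been seen.

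**Working it through.** **1. The plan's own figure.** The Power Analysis gives 100 couples, 50% response and a final sample of 40 to 50 couples. 100 × 0.50 = 50 gives the upper end. The lower end, 100 × 0.80 × 0.50 = 40, needs a loss of about 20% that is not stated. Since 50 is the number of responders, the natural reading of 40 to 50 is responding couples. No alpha, power, effect size or SD is given, so there is no power calculation to reproduce.

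**2. What the paired test estimates.** Let the unaffected mean levels be μF and μM, and the deficits δF and δM. The mean within-couple difference is

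(μF − δF) − (μM − δM) = (μF − μM) − (δF − δM).

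If δF = δM, the deficit vanishes whatever its size. If both deficits are zero but μF ≠ μM, the difference is non-zero. The signed-rank fallback uses the same difference. The algebra needs a common scale. The Methodology gives each sex its own GRISS total, with five sex-specific domains and two shared ones, and the plan does not say which score is paired.

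Numerical check on one simulated set of 100 pairs, shifting both partners by 0, −0.5, −1 and −2 SD: the paired result was t = 0.280, p = 0.780 every time. A one-sample test of the women against a fixed reference went from p = 0.39 to 1.3e-9, 3.6e-22 and 2.1e-43.

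Conversely, take no deficit but a 0.3 SD gap between partners (equal SDs, 100 couples, two-sided 0.05, partner correlation r). The standardised paired effect is 0.3/√(2(1 − r)), that is 0.25, 0.30 and 0.39 for r = 0.3, 0.5 and 0.7. The test then rejects 71%, 84% and 97% of the time.

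**3. Precision of a description of level.** The 95% half-width in SD units is t(0.975, n−1)/√n.
- n = 100: 1.984/10 = 0.198
- n = 80 (100 less an assumed 20%): 1.990/8.944 = 0.223

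**4. What a DAS change analysis could detect.** Assumed: two-sided alpha 0.05 and 80% power, in SDs of the change score. The normal approximation is 2.802/√n within responders and 2.802 × √(1/a + 1/b) between groups of size a and b. The last column uses the noncentral t. The unequal splits are assumptions; they are shown because the plan counts even the smallest improvement category as response, so 50% is uncertain.

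| Comparison | Approximation | Noncentral t |
|---|---|---|
| Within 50 responders | 0.396 | 0.40 |
| Within 40 responders | 0.443 | 0.45 |
| 50 v 50 | 0.560 | 0.57 |
| 40 v 40 | 0.626 | 0.63 |
| 70 v 30 | 0.611 | 0.62 |
| 80 v 20 | 0.700 | 0.71 |

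The 95% half-width for the 50 v 50 difference is 1.984 × √(1/50 + 1/50) = 0.40 SD.

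**5. Direction of change.** The plan defines women's GRISS change as baseline minus 3-month, and men's as follow-up minus baseline. Any DAS change score has to be placed in one convention.

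**The case against.** The best defence is that Aim 1 only sets out to define levels. The paired test needs both partners' baseline GRISS scores, so GRISS levels are readily obtained, and comparing partners is worthwhile in a study built around the male perspective. All of that is fair. What remains is that the hypothesis says lower, nothing is named to be lower than, and the plan does not specify the descriptive summary.

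It can also be said that GRISS touches relationship satisfaction, since the Power Analysis says that the DAS also measures it. That supplies neither a comparator nor a cohesion measure. The Methodology describes GRISS as assessing the sexual relationship.

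The PISQ-12, PFIQ-7 and MESA are likewise repeated at 12 weeks without a planned analysis, so the DAS is not alone. It stands out because the cohesion wording and the sample size both depend on it.

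Stronger readings are tempting but not supported:
- A reader might infer that men do not repeat the DAS. The follow-up set is not itemised, but it comes directly after the women's list, and men complete GRISS and DAS at baseline. This needs a clarifying word only.
- A reader might infer an inflated false-positive rate over many GRISS and DAS comparisons with norms. The plan contains no such comparisons.
- A reader might infer that the partner comparison should move from GRISS to the DAS. That is a preference; nothing in the documents requires it.

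**Conclusion.** The point holds and should be fixed. Followed exactly, the plan can neither support nor refute Aim 1's hypothesis, and Aim 2's predicted gain in relationship satisfaction is analysed through GRISS change only. The first conclusion follows from the design and needs no assumption about alpha, power or correlation; the exact cancellation of a shared deficit assumes a common scale.

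The sizes do rest on assumptions: two-sided alpha 0.05, 80% power, 80 to 100 couples and the response splits shown. On these, levels can be estimated to within about 0.20 to 0.22 SD. Change in DAS would be detectable at 0.40 to 0.45 SD within responders and 0.57 to 0.71 SD between response groups.

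A reader might infer that the trial's main result is undermined. It is not: the primary outcome is change in overall GRISS, and its analysis does not depend on the Aim 1 test or on the DAS.

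**What to change.** **Aim 1.**
- Report baseline GRISS (female and male versions separately) and DAS (total and subscales, by sex) with 95% confidence intervals in all enrolled couples.
- Restate the hypothesis as descriptive, in line with the aim, in a dated and disclosed amendment. The protocol dates from 2011 and was revised in 2018, so an undated change could look post hoc.
- Keep the word lower only if a reference for each instrument and sex is named before analysis and is described as not a concurrent control. The documents give no such values.
- Keep the paired test, label it partner discordance, and say which GRISS score it uses.

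**Aim 2.**
- Add change in DAS as a secondary analysis for each sex, both within responders and between responders and non-responders, with 95% confidence intervals.
- State one direction of change for all scores.
- Say in a few words that the men's follow-up set includes the DAS.

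**Cost.** Amended wording and a little more analysis, on data that the protocol already plans to collect. The price is a weaker Aim 1 claim and imprecise DAS change estimates (half-width about 0.40 SD at 50 v 50).

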The Golombok-Rust Inventory of Sexual Satisfaction (GRISS) is a 28-item self-administered questionnaire that was developed by sex therapists to assess the quality of the sexual relationship of a heterosexual couple. The survey, which takes approximately 15 minutes to complete, evaluates 12 domains, 5 of which are female-specific, 5 male-specific, and 2 non-gender specific. The GRISS receives a Grade A recommendation from the International Continence Society for its appropriateness as a tool for evaluating sexual function as a dimension of overall health-related quality of life among patients with pelvic floor disorders.

The female version produces a Total GRISS Female Score as well as subscales of:

- *Anorgasmia* - the extent to which a woman is able to attain orgasm.
- *Vaginismus* - the extent of any tightness around the vagina that interferes with sex.
- *Non-communication* - The extent to which a couple are able to talk about any sexual problems.
- *Infrequency* - The number of times a week (or less) on which sexual intercourse takes place.
- *Female Avoidance* - The extent to which a female partner is actively avoiding having sex.
- *Female Non-sensuality* - The extent to which a female partner gains pleasure from touching and caressing.
- *Female Dissatisfaction* - The extent to which a woman is dissatisfied with their sexual partner.

The male version produces a Total GRISS Male Score as well as subscales of:

- *Impotence* - the extent of any failure by a man to achieve an erection.
- *Premature ejaculation* - the extent to which a man has the tendency to ejaculate too soon.
- *Male Avoidance* - The extent to which a male partner is actively avoiding having sex.
- *Male Non-sensuality* - The extent to which a male partner gains pleasure from touching and caressing.
- *Male Dissatisfaction* - The extent to which a man is dissatisfied with their sexual partner.
- *Non-communication & Infrequency* – Same as the female version

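### Aim 1 tests a female-minus-male GRISS difference without saying which score is used or why the separate female and male totals can be treated as one metric

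*Combined protocol and SAP*

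**What the plan says.** The only analysis specified for Aim 1 is in the Statistical Analysis Plan: baseline GRISS "scores will be compared between matched male and female partners using a paired samples" t-test. The quantity analysed is a within-couple subtraction: "The difference between female and male responses will be assessed for normality using a QQ plot". If the assumptions fail, a Wilcoxon signed-rank test may be used to confirm the conclusion.

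The GRISS description under Methodology says that the instrument "evaluates 12 domains, 5 of which are female-specific, 5 male-specific, and 2 non-gender specific". It then names two totals. One sentence begins "The female version produces a Total GRISS Female Score as well as subscales of" and lists seven subscales. The other begins "The male version produces a Total GRISS Male Score as well as subscales of" and also leads to seven. For non-communication and infrequency, the male list says "Same as the female version".

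The hypothesis under Specific Aim #1 concerns couples, not a contrast between partners: "Couples with (female partner) UUI will have lower levels of relationship satisfaction and sexual function".

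Both partners also complete the DAS. Of this the Methodology section says: "The DAS consists of a 32-item self-administered questionnaire that is not gender specific". The Statistical Analysis Plan contains no analysis of DAS data.

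**The concern.** A paired test against zero can be interpreted only if zero means that the two partners are equally affected. That requires both numbers to be on one metric. The protocol describes two totals built from partly different content: anorgasmia and vaginismus enter on one side, impotence and premature ejaculation on the other. It does not state that equal totals mean equal sexual function.

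If the forms differ in level because of their content or scoring, the mean difference picks up that offset along with any real difference between partners, and the test cannot separate the two. The signed-rank fallback works on the same within-couple differences, so it does not help. The plan has no other Aim 1 analysis to fall back on.

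**Working it through.** **1. Subscale count (from the GRISS description under Methodology).** The stated count is reproduced: 5 female-specific + 5 male-specific + 2 shared = 12 domains, and 5 + 2 = 7 per form.

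| Relation between forms | Female form | Male form | Number per form |
|---|---|---|---|
| Shared | Non-communication, infrequency | Non-communication, infrequency | 2 of 7 |
| Parallel, separately defined | Female avoidance, non-sensuality, dissatisfaction | Male avoidance, non-sensuality, dissatisfaction | 3 of 7 |
| No counterpart | Anorgasmia, vaginismus | Impotence, premature ejaculation | 2 of 7 |

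So 5 of 7 (71%) are sex-specific as labelled, but by construct name only 2 of 7 (29%) have no counterpart.

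**2. Which score is tested.** The Aim 1 text says only GRISS scores. It does not say total or subscale, raw or standardised. The Power Analysis names the change in the overall score as the primary outcome, and the Aim 2 text specifies the overall score. Aim 1 describes one test and one difference, so the total is the natural reading, but it is not stated.

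**3. Sensitivity of the test to a form offset.** This is an illustration. The documents give no offset, SD, alpha or power.

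Inputs: n = 100 couples (the recruitment target) or n = 50 (100 × 0.50, the upper end of the stated final sample). Assumed: two-sided 5% level, partners truly equally affected, and a constant offset c between forms in units of the SD of the paired difference.

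Formula (normal approximation, far tail negligible): rejection probability ≈ P(Z > 1.96 − c√n).

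- n = 100, c = 0.2: c√n = 2.00, P(Z > −0.04) ≈ 52%
- n = 100, c = 0.3: c√n = 3.00, P(Z > −1.04) ≈ 85%
- n = 50, c = 0.2: c√n = 1.41, P(Z > 0.55) ≈ 29%
- n = 50, c = 0.3: c√n = 2.12, P(Z > −0.16) ≈ 56%
- Either n, c = 0: 5%

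**4. The same check on another scale.** Here the offset is in SDs of a single score, with an assumed within-couple correlation of 0.2 to 0.6. The SD of the difference is √(2(1 − ρ)) single-score SDs, i.e. 1.26 at ρ = 0.2 and 0.89 at ρ = 0.6. Rejection rates from the noncentral t distribution:

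| Offset (SD of one score) | 100 couples | 50 couples |
|---|---|---|
| 0.1 | 12–20% | 9–12% |
| 0.25 | 50–79% | 28–49% |
| 0.5 | 97.5% to nearly 100% | 78–97% |

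The two scalings agree: 0.25 SD of one score is 0.25/1.26 = 0.20 to 0.25/0.89 = 0.28 SD of the difference.

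**5. Scope.** Both Aim 2 comparisons are of change scores within one sex (women by response; male partners by the woman's response). They never mix the two forms.

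**The case against.** The strongest reply is that the plan is under-specified rather than wrong. The Aim 1 text does not say that totals are used, and it leaves out the word that marks the overall score in Aim 2. Whether female and male scores share a metric, for example through scoring against own-sex norms, depends on the scoring rules of the cited instrument, which the documents do not reproduce. Three of the five sex-specific subscales have a namesake on the other form. No hypothesis claims that one partner is worse off. The rejection rates follow from whatever offset is put in, and nothing in the documents shows that an offset exists.

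All of this stands, and it limits the point. A reader might infer that the subtraction can never be a difference on one scale, or that any significant result would be an artefact of unlike content. The documents do not support either: they neither state nor exclude standardisation within sex, and they do not fix the score. Nor does the 5-of-7 count mean that five subscales are unlike in construct.

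The reply does not remove the problem. Matching names do not establish equal scaling, and no equivalence is claimed. If subscales were intended, none is named. Under either reading, the text does not support interpreting the result as a difference between partners.

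It is also fair to say that the obvious substitutes have limits. Infrequency and non-communication describe the couple, so pairing them mainly shows whether partners report alike. The DAS measures relationship adjustment, not sexual function.

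**Conclusion.** The point holds as a gap in specification and justification. The SAP does not define the GRISS score that enters the Aim 1 test and gives no reason to treat the two totals as commensurable. Until it does, the sign and significance of a difference in totals say nothing reliable about which partner is worse off, and a null result does not show that they are equally affected.

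The size of the effect is unknown. The 52–85% (100 couples) and 29–56% (50 couples) rejection rates rest entirely on assumed offsets of 0.2 to 0.3 SD of the paired difference. They show how sensitive the test would be, not that the forms differ. With no offset the rate is 5%.

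Only Aim 1 is affected. It would be wrong to extend the point to the primary outcome: the Aim 2 comparisons stay within sex, and no sample-size figure changes. This is a change the sponsor should make, and a cheap one.

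**What to change.** In the Aim 1 paragraph of the Statistical Analysis Plan:

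1. Report the baseline Total GRISS Female Score and Total GRISS Male Score separately, each with a mean and confidence interval. This suits an aim that sets out to describe levels. Base no inferential conclusion on their raw difference.
2. Make the partner comparison on the DAS total, stating how that total is formed from the questionnaire. Both partners complete the DAS on a form that is not sex-specific, and it covers the relationship satisfaction named in Aim 1 that the SAP currently leaves unanalysed.
3. Pair the two shared GRISS subscales, non-communication and infrequency, as secondary measures. Interpret them as agreement between partners' reports of the couple, not as showing who is worse off.
4. If a contrast of GRISS totals is kept, pre-specify scores standardised within sex, name the reference norms, and interpret the result as distance from own-sex norms. The norms must come from outside the study sample: standardising each sex to its own sample mean makes the average difference zero by construction.

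Cost: SAP wording only, since all the scores are already to be collected. The downside is that there is no single overall GRISS figure for the difference between partners, and more than one paired comparison to report. Naming the DAS total as the main comparison and the two subscales as secondary keeps that manageable.
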